### 9.9.1. Response Criteria

Disease response will be assessed using IMWG ([Kumar 2016](#)). There is no maximum treatment duration. Disease response will be assessed centrally by an independent IRC ([Section 7.2](#)). Definitions of individual response criteria are provided in [Appendix 3](#).

### 9.9.2. Quality of Life Assessment

Health-related QoL and potential for improvement over the course of the study will be assessed by the FACT-MM patient-reported outcome questionnaire that is specifically relevant to MM. Additional information on the FACT-MM is provided in [Section 13.3.4](#).

Patients should complete the FACT-MM assessment *before* they undergo any study related procedure, including other study related evaluations, discussions with medical personal, physician and study treatment administration.

## **10. DISCONTINUATION CRITERIA**

### **10.1. Early Discontinuation of the Study**

The study may be discontinued at the sole discretion of the Sponsor for any reason, including medical or ethical reasons affecting the continued performance of the study, or difficulties in the recruitment of patients.

The DSMB will inform the sponsor if a safety signal is detected (see Section 7.2). The sponsor, in conjunction with appropriate regulatory authorities, would then decide if the trial should be modified or terminated. If this occurs, the sponsor will notify IRB/REB/ECs and investigators.

### **10.2. Early Discontinuation of Individual Patients**

The Investigator may remove a patient from study treatment at his/her discretion for any of the following reasons:

- Disease progression defined according to IMWG for progression of MM, including confirmatory analysis to document progression. Disease progression must be confirmed by the IRC prior to discontinuation of the study treatment
- Unacceptable AE(s) or failure to tolerate the study treatment
- Patient decides to discontinue study therapy
- Any medically appropriate reason or significant protocol violation, in the opinion of the Investigator

Reasons for discontinuation must be clearly documented in the source and in the study CRFs, including reasons for patient withdrawal and Investigator decision to discontinue the patient.

Patients may discontinue study treatment for any reason. Patients who elect to discontinue study treatment should be encouraged to continue in the study so that follow-up information on disease progression and survival status may be obtained. However, patients may elect to withdraw consent and decline further participation in the trial.

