
Criteria for Treatment Discontinuation:
 
At the discretion of the Investigator, the Investigator may remove a patient from study treatment for any of the following reasons:
 

• Disease progression

• Unacceptable AE(s) or failure to tolerate the study treatment

• Patient decides to discontinue study therapy and withdraws consent

• Any medically appropriate reason or significant protocol violation, per the Investigator.

 
Patients may decide to discontinue study treatment for any reason. Patients who elect to discontinue study treatment should be encouraged to continue in the study so that follow-up information on disease progression and survival status may be obtained. However, patients may elect to withdraw consent and decline further participation in the study. The reason for discontinuation should be clearly documented. If clinical or biological progression, study data must be available. If the patient withdraws consent or is removed by the study Investigator, the reason for withdrawal should be documented.
		

Statistical Methods:
 
CCI
 
[REDACTED]
		

Sponsor: Karyopharm Therapeutics Inc.	Investigational Product: Selinexor (KPT-330)	Developmental Phase: Phase 2b

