In select cases (e.g., for patients showing SD or PR and tolerating treatment particularly well), the selinexor dose may be increased by 20 mg after consultation with the Medical Monitor. The dose level for an individual patient may be escalated based on efficacy considerations only after a minimum of 2 cycles of study therapy. However, in no case may the dose for any patient exceed 70 mg/m^2. Prior to any potential dose increase, the body surface area (BSA) for the patient will be calculated and an individual patient's dose may not be increased if it would result in a dose  $> 70$  mg/m^2.

In Part 2, MM-specific assessments (i.e., SPEP, UPEP, serum/urine immunofixation, quantitative Ig levels, serum FLC, and bone marrow aspirate) must be confirmed by a central laboratory to confirm CR or sCR, and select VGPR, per IMWG. Additional information is provided in the *Study Manual*.

The Investigator may remove a patient from study treatment using criteria described in Section 10.2. Patients may decide to discontinue study treatment for any reason. Patients who elect to discontinue study treatment should be encouraged to continue in the study so that follow-up information on disease progression, other antineoplastic therapy, symptoms and survival status may be obtained. However, patients may elect to withdraw consent and decline further participation in the trial at any time.

The Investigator must determine the primary reason for a patient's discontinuation of study treatment and record this information on the electronic case report form (eCRF). Patients who are prematurely withdrawn from study treatment are not eligible to re-initiate study treatment on this protocol at a later date.

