## **7.3. Independent Review Committee**

An Independent Review Committee (IRC), will review disease assessment data to independently assess disease response. The IRC will review data that will be used for the analysis of the primary endpoint. The IRC's assessments of disease response and time to progression (TTP) will be used as the basis for the evaluation of the primary endpoint.

The IRC membership, functioning, and procedures (including resolution of any disagreements with Investigators regarding disease assessments) will be described in the *IRC Charter*.

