Patients may receive a study treatment holiday at any time during the four-week cycles, following prior consultation with the Medical Monitor.

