4.2.1. Duration of Response (DOR)

4.2.1.1. Definition

DOR is defined for patients with a confirmed PR or better as the duration from first observation of at least PR to time of IRC-determined PD or death due to disease progression, whichever occurs first. The censoring method for DOR is the same as the censoring method for TTP in Table 4-2.

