4.2.2. Best Overall Response and Clinical Benefit Rate (CBR)

4.2.2.1. Definition

The number and percentage of patients in the individual response categories (MR, PR, VGPR, CR, sCR) based on best response will be calculated respectively.

CBR is defined as the proportion of patients who achieve a confirmed MR or better, i.e., MR, PR, VGPR, CR, sCR. Duration of clinical benefit is defined as the duration from first observation of at least MR to time of IRC-determined PD or death due to disease progression, whichever occurs first. Responders without IRC-determined PD or death due to disease progression will be censored at the censored date for TTP.

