4.2.2.2. Analysis Methods

The rate of CBR and the 2-sided, exact 95% CI will be calculated using the mITT population. Median duration of clinical benefit with 95% CI will be estimated based on the Kaplan-Meier method. The Kaplan-Meier curve for the duration of clinical benefit will be provided.

As supportive analyses, CBR rate and 95% CI will be calculated:

- Using the BCLPD-ref, CLPD-ref, BCPD-ref, CPD-ref, all penta-ref, high-risk, EE, PP, Part 1 – Quad, Part 1 – Penta, doses populations respectively.
- In patients with R-ISS for MM stage I, II, and III respectively
- In US vs. non-US patients
- In FLC MM vs. non-FLC MM patients.

Median duration of clinical benefit with 95% CI will be calculated in these analysis populations and subgroups when sufficient data exist.

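### Protocol 10.2 makes a stop for progression wait for the IRC, and the visible SAP gives DOR and duration of clinical benefit no supportive analysis for stops on investigator-assessed progression

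*Protocol*

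**What the plan says.** **Stopping treatment.** Protocol 7.1 makes Section 10.2 the operative text: "The Investigator may remove a patient from study treatment using criteria described in Section 10.2". Section 10.2 opens by leaving removal to the investigator's discretion. Its first listed reason, progression, then carries the condition "Disease progression must be confirmed by the IRC prior to discontinuation of the study treatment". Its last reason is any medically appropriate one in the investigator's opinion. The synopsis (Criteria for Treatment Discontinuation) says "the Investigator may remove a patient from study treatment for any of the following reasons" and lists disease progression with no IRC step. Section 7.3 describes the committee's job as endpoint review: "The IRC will review data that will be used for the analysis of the primary endpoint". It says nothing about stopping drug and leaves disagreements with investigators to the IRC Charter, which is not among the documents. Section 11.1.3 gives another route: "Patients may receive a study treatment holiday at any time during the four-week cycles, following prior consultation with the Medical Monitor".

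**Durations.** SAP 4.2.1.1 ends DOR at IRC-determined PD or death due to progression, and adds "The censoring method for DOR is the same as the censoring method for TTP in Table 4-2". For duration of clinical benefit, SAP 4.2.2.1 says "Responders without IRC-determined PD or death due to disease progression will be censored at the censored date for TTP". Table 4-2 lists documented treatment discontinuation among the censoring triggers and dates the censoring to the last adequate assessment before it. SAP Section 4 calls both durations key secondary endpoints.

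**Supportive analyses.** SAP 4.2.4.2 and 4.2.5.2 each plan an investigator-assessed version, for PFS and TTP respectively. The DOR list in 4.2.1.3 holds only other populations and subgroups. So does 4.2.2.2, which says of the other duration: "Median duration of clinical benefit with 95% CI will be calculated in these analysis populations and subgroups when sufficient data exist".

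**The concern.** There are two linked points.

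The first is operational. A site that follows 10.2 to the letter waits for a committee ruling before it stops drug for progression, although the same section leaves the decision to the investigator. The cost would be extra exposure in a progressing patient, or a stop recorded under some other reason.

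The second is statistical. A responder whom the investigator takes off drug for progression, and for whom the IRC has no PD on or before the stop, leaves the DOR risk set as censored. The reason for leaving is apparent worsening, so the censoring is plausibly informative and would tend to lengthen the Kaplan-Meier median. The same holds for duration of clinical benefit.

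The points interact. If 10.2 is obeyed, a stop recorded for PD already has IRC-confirmed PD and counts as an event. Once the sentence goes, stops on investigator-assessed PD alone become more likely, so the deletion and the added analysis belong together.

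**Working it through.** **Step 1. Stopping rule, texts side by side.**

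| Place | Who decides on a stop for PD | IRC step |
|---|---|---|
| Synopsis | Investigator's discretion | None stated |
| 7.1 | Refers to 10.2 | None of its own |
| 7.3 | Not addressed | Endpoint review only |
| 10.2, lead-in | Investigator's discretion | None stated |
| 10.2, first reason | Waits for the IRC | Required |

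The condition appears once, in the section sites are told to use. The tension is within 10.2 itself and with the synopsis; 7.3 is silent.

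**Step 2. How Table 4-2 treats a responder stopped on investigator-assessed PD.**

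- IRC-determined PD dated on or before the stop, with no gap of 65 days or longer: event. PD that rests on two samples is dated to the earlier one (SAP Section 4), so a confirming sample taken after the stop does not lose the event.
- No IRC-determined PD, then death due to progression without a gap of 65 days or longer: an event under the death row. That row overlaps with the discontinuation row when the death follows the stop, and the table does not say which prevails.
- Neither: censored at the last adequate assessment before the stop.

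The third group is the one at issue.

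**Step 3. Size, illustration only.** The plan states no figure to reproduce, and the documents give no discordance rate. Inputs:

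- Median DOR m = 5 months, the approximate Part 1 value (Synopsis, Rationale for Expansion).
- Exponential durations (assumption).
- A random share f of true progressions becomes censored 28 days before the event date (assumption; 28 days is the assessment interval in SAP 4.2.5.2).

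With rate λ = ln 2 / 5 and d = 28 / 30.4375 = 0.92 months, the event density at t is (1 − f)λe^(−λt). The proportion at risk is e^(−λt)[(1 − f) + f·e^(−λd)]. The apparent hazard is their ratio, so

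apparent median = m × [1 + f/(1 − f) × e^(−λd)], where e^(−λd) = 2^(−0.92/5) = 0.880.

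| f (assumed) | Apparent median, months | Bound if censored at the stop itself, m/(1 − f) |
|---|---|---|
| 5% | 5 × (1 + 0.0526 × 0.880) = 5.23 | 5.26 |
| 10% | 5 × (1 + 0.1111 × 0.880) = 5.49 | 5.56 |
| 20% | 5 × (1 + 0.25 × 0.880) = 6.10 | 6.25 |

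A simulation of 2,000,000 patients gave 5.22, 5.48 and 6.10. When progression is seen only at 28-day visits, the median moves in steps of one visit. With censoring at the preceding visit it stayed at 5.5 months for f of 5% and 10%, and read 6.4 at 20%.

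**Step 4. Compare with sampling error.** Table 3 of the Protocol gives 20% ORR and 40% CBR in Part 1 penta-refractory patients, and the target size is 122.

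- Responders: 0.20 × 122 = 24.4. A share of 10% to 20% is about 2 to 5 patients.
- Clinical-benefit patients: 0.40 × 122 = 48.8. A share of 10% to 20% is about 5 to 10 patients.

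With a true median of 5 months and no other censoring, the 2.5 to 97.5 percentile range of the sample median is about 2.5 to 8.0 months for n = 24 and 3.3 to 7.3 months for n = 49. The second range borrows the 5-month median, since the documents give none for clinical benefit. The shift of about 0.2 to 1.1 months in Step 3 lies well inside both ranges.

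**The case against.** **The synopsis is a summary and 10.2 is the full rule.** No current section says IRC confirmation is not needed, so this is a difference in detail rather than a flat contradiction. That stands: a reader might infer that the protocol contradicts itself across sections, and the documents support less. What remains is the friction inside 10.2. The summary of changes for version 6.0, in explaining a deletion from 7.3, says a stop does not need IRC confirmation. That is context for choosing deletion over spreading the step to other sections; the point does not rest on it.

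**A progressing patient is not trapped on drug.** The investigator may stop for any medically appropriate reason or arrange a treatment holiday, and the patient may stop at any time. This also stands, and it softens the safety side. It equally means that stops on the investigator's judgment can happen under the current text, so 10.2 does not close the censoring gap.

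**Counting investigator-only PD as an event presumes that the investigator was right and the IRC wrong.** True. That is why it should be supportive, beside the IRC-based analysis.

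**Investigator-assessed TTP and PFS already show discordance.** They show it from the start of treatment in all patients. Neither measures time from first response in responders.

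**Redactions may hide the analysis.** The SAP change log has a blacked-out entry for 4.2.1.3, and SAP 4.1.3 and 4.3 and parts of Protocol Section 9 are also hidden. The current 4.2.1.3 and 4.2.2.2 lists are readable and contain no such analysis, but one elsewhere cannot be fully excluded.

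**Conclusion.** The point holds as a minor one. Section 10.2 contains a condition that sits badly with its own lead-in and with the synopsis, and that can delay a stop if taken literally. DOR and duration of clinical benefit lack, in the visible text, the kind of check on assessor that PFS and TTP have.

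Three stronger readings are not supported:

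- That the reported DOR will be biased by a known amount. No discordance rate is given. The 5.2, 5.5 and 6.1 months rest on an exponential 5-month median, assumed shares of 5%, 10% and 20%, and every discordant stop being a true progression. The shift is likely smaller than sampling error.
- That the primary result is at risk. The ORR test counts confirmed IRC responses and does not use the duration censoring. DOR is summarised descriptively (SAP 4.2.1.2).
- That every stop on investigator-assessed PD is censored. An IRC PD dated on or before the stop is an event, and death due to progression may be.

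Confidence is medium because of the redactions and the unavailable IRC Charter.

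**What to change.** 1. Delete from Protocol 10.2 the sentence requiring IRC confirmation before treatment is stopped. The rest of the section can stay.
2. Add to SAP 4.2.1.3 and 4.2.2.2 one supportive analysis in the same IRC-defined responders (PR or better for DOR, MR or better for clinical benefit). It counts investigator-assessed PD that leads to a treatment stop as an event at the investigator's PD date. This is a hybrid: it keeps the IRC's definition of response and changes only how these stops are handled. It resembles, but is not the same as, the investigator-assessed PFS and TTP analyses.

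The IRC-based definitions remain the main analyses, and the SAP's reference to Protocol V5.0 needs no change for this purpose. The cost is one deleted sentence and one extra analysis for two endpoints, using investigator PD dates already needed for PFS and TTP. It may show slightly shorter medians.

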## **11. TREATMENT**

Selinexor study medication will be in the form of a coated, immediate-release tablet for oral administration. Selinexor tablets will be supplied as single-strength (20 mg) tablets in wallet-size blister packs. Dexamethasone 20 mg will be given with each dose of selinexor.

Additional information is provided in Section 11.1.3.

### **11.1. Dosing and Administration**

#### **11.1.1. Dose Modifications**

All dosing modifications should be discussed with the study Medical Monitor prior to implementing the dosing change.

### 11.1.2. Labeling

All drug containers will be labeled in accordance with current International Conference on Harmonization (ICH), GCP, and regulatory agency-specific requirements (e.g., FDA, MHRA). Medication labels will include the medication name, storage conditions, and batch number, and will comply with language and legal requirements of the US.

### 11.1.3. Dosing Information

Selinexor will be administered as a fixed oral selinexor dose of 80 mg twice weekly (e.g., Monday and Wednesday or Tuesday and Thursday, etc.) on Weeks 1-4 of each four-week cycle. For doses on non-clinic days, the patient will be provided with doses by the hospital pharmacy to take home.

Dexamethasone 20 mg will be given with each dose of selinexor. For patients with partial intolerance to glucocorticoids (as determined by the Investigator), a minimum dose of 10 mg dexamethasone is permitted. If any patient is not able to tolerate this dose, then a potential discontinuation or further decrease in dosage would be allowed after a discussion with the Medical Monitor on a case by case basis. Dexamethasone will be provided to take home in the form of tablets.

In select cases (e.g., for patients showing SD, MR, or PR and tolerating treatment particularly well), the selinexor dose may be increased by 20 mg after discussion with the sponsor. The dose level for an individual patient may be escalated based on efficacy considerations after a minimum of 2 cycles of study therapy. However, in no case may the dose for any patient exceed 70 mg/m^2. Prior to any potential dose increase, the BSA for the patient should be calculated. Patients with may have their dose increased if it would result in a dose >70 mg/m^2 [REDACTED]

Selinexor should be given with, or within 30 minutes of, solid food consumption (to optimize tolerability) together with at least 120 mL (4 ounces) of fluids (water, juice, etc.) For details of drug formulation, preparation, and administration, please refer to [Appendix 4](#).

Selinexor tablets should be swallowed whole and should not be crushed to avoid increased risk of dermatologic toxicity if the powder comes in contact with skin.

Compliance to study treatment will be assessed by the Investigator or delegate at each patient visit and recorded in source documents after discussion with the patient and drug accountability. The date will be recorded as per study drug schedule. The Investigator or the designee will account for the number of tablets dispensed against those returned by the patient. Any deviations and missed doses will be recorded in the eCRF and drug accountability logs for verification with the reasons. The Investigator / designee will attempt to ensure complete compliance with the dosing schedule by providing timely instructions to the patients.

Patients may receive a study treatment holiday at any time during the four-week cycles, following prior consultation with the Medical Monitor.

#### **11.1.4. Dose Modifications for Patients with VGPR**

In an effort to improve long-term disease control and tolerability, this protocol allows for dose reductions in patients with very good anti-tumor activity of selinexor. Thus, for patients who achieve  $\geq$  VGPR for  $\geq$  6 months and who, in the opinion of the Investigator may benefit from dose reduction(s), the following modifications may be considered: (a) The dose of dexamethasone may be reduced by 40% or (b) the dose of selinexor may be reduced by 20 mg or (c) the frequency of selinexor may be reduced to once weekly, after consultation with the Medical Monitor. In general, dexamethasone should always be given on the day(s) of selinexor dosing. Patients whose doses are reduced under this schema should have appropriate MM markers monitored at least every two weeks (e.g., with FLC) so that dose may be re-escalated to their initial dose if evidence of progression occurs. These monitoring studies may be done at local laboratories.

#### **11.1.5. Dose Reduction Guidelines for Toxicity**

Toxicity will be graded according to CTCAE v.4.03 criteria; the therapy modifications described below are applied according to this severity grading.

If more than one type of toxicity occurs concurrently, the most severe grade will determine the modification.

Re-escalation of the study drug is allowed as outlined in the sections that apply for the specific toxicity. If drug-related toxicity requires a treatment delay of more than 28 days, the patient is taken off protocol treatment.

Each dose modification or treatment delay must be documented in the eCRF, including the respective reason.

Based on observations from the ongoing Phase 1 studies in patients with advanced hematological and solid tumors, selinexor shows a reasonably wide therapeutic range, with activities from  $\sim 6$  mg/m^2 to  $\geq 60$  mg/m^2. Therefore, in order to optimize specific anti-tumor activity and the patient's tolerability, dose reductions and/or schedule modifications will be allowed as described in [Table 5](#) and [Table 6](#). Patients should also be treated aggressively with supportive care to reduce toxicities.

For all Grade  $\geq 3$  hematological or non-hematological AEs that are NOT selinexor related, after consultation with the Medical Monitor and at the discretion of the Investigator, selinexor dosing may be maintained, provided that the patient can continue to take the agent by mouth.

